8.5 Medical Monitoring

It is the responsibility of the Principal Investigator to oversee the safety of the study at his/her site. This safety monitoring will include careful assessment and appropriate reporting of adverse events as noted above, as well as the construction and implementation of a site data and safety-monitoring plan (see section 9 Auditing, Monitoring and Inspecting). Medical monitoring will include a regular assessment of the number and type of serious adverse events.

Safety Monitoring will be performed by [name], who is not a study investigator. The CRFs and any relevant source documents will be sent to the medical safety monitor (as above) who will review them after treatment is complete for subject 1, 3, 10 and 20.

The research coordinator will complete the appropriate report form and logs; assist the PI to prepare reports and notify the IRB, FDA, and/or safety monitor of all Unanticipated Problems/SAE's.

The research coordinator and co-principal investigators will confirm that all Adverse effects (AE) are correctly entered into the AE log by the coordinator; be available to answer any questions that the coordinators may have concerning AEs; notify the IRB and FDA of all Unanticipated Problems/SAEs and AEs as appropriate. All assessments of AEs will be made by a licensed medical professional who is an investigator on the research.

Complications will be assessed by the co-PIs, categorized into major and minor categories and recorded on the CRF. CRFs and appropriate source documents will be made available to this individual for bi-monthly (every 2 months) review to ensure completeness of data collection. Any discrepancies will be immediately addressed by the co-PIs. All adverse events will be recorded and then summarized for inclusion in the final manuscript.

Data monitoring will be performed by an individual who is not a study investigator. CRFs and appropriate source documents will be made available to this individual for review to ensure completeness of data collection. Any discrepancies will be immediately addressed by the co-PIs.

- Verify receipt of all documents and supplies needed to conduct study
- Informed consent obtained for each participant
- Source document verification 100%
- CRF completion
- Investigational product accountability
- Check and review of the regulatory binder and all essential documents
- Clinical supply inventory
- SAE reporting
- Protocol amendment and their approval by the IRB
- Significant protocol deviations

- Personnel changes
- Updated regulatory documentation
- Any other issue as deemed important to the conduct of the study

9 Data Handling and Record Keeping

9.1 Confidentiality

Information about study subjects will be kept confidential and managed according to the requirements of the Health Insurance Portability and Accountability Act of 1996 (HIPAA). Those regulations require a signed subject authorization informing the subject of the following:

- What protected health information (PHI) will be collected from subjects in this study
- Who will have access to that information and why
- Who will use or disclose that information
- The rights of a research subject to revoke their authorization for use of their PHI.

In the event that a subject revokes authorization to collect or use PHI, the investigator, by regulation, retains the ability to use all information collected prior to the revocation of subject authorization. For subjects that have revoked authorization to collect or use PHI, attempts should be made to obtain permission to collect at least vital status (i.e. that the subject is alive) at the end of their scheduled study period.

9.2 Source Documents

Source data is all information, original records of clinical findings, observations, or other activities in a clinical trial necessary for the reconstruction and evaluation of the trial. Source data are contained in source documents. Examples of these original documents, and data records include: hospital records, clinical and office charts, laboratory notes, memoranda, subjects' diaries or evaluation checklists, pharmacy dispensing records, recorded data from automated instruments, copies or transcriptions certified after verification as being accurate and complete, microfiches, photographic negatives, microfilm or magnetic media, x-rays, subject files, and records kept at the pharmacy, at the laboratories, and at medico-technical departments involved in the clinical trial.

9.3 Case Report Forms

The study case report form (CRF) is the primary data collection instrument for the study. All data requested on the CRF must be recorded. All missing data must be explained. If a space on the CRF is left blank because the procedure was not done or the question was not asked, write "N/D". If the item is not applicable to the individual case, write "N/A". All entries should be printed legibly in black ink. If any entry error has been made, to correct such an error, draw a single straight line through the incorrect entry and enter the correct data above it. All such changes must be initialed and dated. **DO NOT ERASE OR WHITE OUT ERRORS.** For clarification of illegible or uncertain entries, print the clarification above the item, then initial and date it.

9.4 Records Retention

It is the investigator's responsibility to retain study essential documents for at least 2 years after the last approval of a marketing application in their country and until there are no pending or contemplated marketing applications in their country or at least 2 years have elapsed since the formal discontinuation of clinical development of the investigational product. These documents should be retained for a longer period if required by an agreement with the sponsor. In such an instance, it is the responsibility of the sponsor to inform the investigator/institution as to when these documents no longer need to be retained.

10 Study Monitoring, Auditing, and Inspecting

10.1 Study Monitoring Plan

This study will be monitored by an independent monitor from outside of UNC. The investigator will allocate adequate time for such monitoring activities. The Investigator will also ensure that the monitor or other compliance or quality assurance reviewer is given access to all the above noted study-related documents and study related facilities (e.g. pharmacy, diagnostic laboratory, etc.), and has adequate space to conduct the monitoring visit.

10.2 Auditing and Inspecting

The investigator will permit study-related monitoring, audits, and inspections by the IRB, the sponsor, government regulatory bodies, and University compliance and quality assurance groups of all study related documents (e.g. source documents, regulatory documents, data collection instruments, study data etc.). The investigator will ensure the capability for inspections of applicable study-related facilities (e.g. pharmacy, diagnostic laboratory, etc.).

Participation as an investigator in this study implies acceptance of potential inspection by government regulatory authorities and applicable University compliance and quality assurance offices.

11 Ethical Considerations

This study is to be conducted according to US and international standards of Good Clinical Practice (FDA Title 21 part 312 and International Conference on Harmonization guidelines), applicable government regulations and Institutional research policies and procedures.

This protocol and any amendments will be submitted to a properly constituted independent Ethics Committee (EC) or Institutional Review Board (IRB), in agreement with local legal prescriptions, for formal approval of the study conduct. The decision of the EC/IRB concerning the conduct of the study will be made in writing to the investigator and a copy of this decision will be provided to the sponsor before commencement of this study. The investigator should provide a list of EC/IRB members and their affiliate to the sponsor.

All subjects for this study will be provided a consent form describing this study and providing sufficient information for subjects to make an informed decision about their participation in this study. This consent form will be submitted with the protocol for review and approval by the EC/IRB for the study. The formal consent of a subject, using the EC/IRB-approved consent form, must be obtained before that subject undergoes any study procedure. The consent form must be signed by the subject or legally acceptable surrogate, and the investigator-designated research professional obtaining the consent.

12 Study Finances

12.1 Funding Source

The radiology department will be using internal funds. Hameln Pharma GmbH will be providing study drug.

12.2 Conflict of Interest

Any investigator who has a conflict of interest with this study (patent ownership, royalties, or financial gain greater than the minimum allowable by their institution, etc.) must have the conflict reviewed by a properly constituted Conflict of Interest Committee with a Committee-sanctioned conflict management plan that has been reviewed and approved by the study sponsor prior to participation in this study. All University of UNC investigators will follow the University conflict of interest policy.

13 Publication Plan

Neither the complete nor any part of the results of the study carried out under this protocol, nor any of the information provided by the sponsor for the purposes of performing the study, will be published or passed on to any third party without the consent of the study sponsor. Any investigator involved with this study is obligated to provide the sponsor with complete test results and all data derived from the study.

14 References

1. Sieber MA1, Lengsfeld P, Walter J, Schirmer H, Frenzel T, Siegmund F, Weinmann HJ, Pietsch H., Gadolinium-based contrast agents and their potential role in the pathogenesis of nephrogenic systemic fibrosis: the role of excess ligand. *J Magn Reson Imaging*. 2008 May;27(5):955-62 doi: 10.1002/jmri.21368

15 Appendices

- A. Table of Events
- B. Visual Analog Pain Scale
- C. Quality of Life scale
- D. Copy of Consent Form

Time and Events Table:

	Pre-treatment Visit 0	V 1 Day 1	V 2 Day 2	V 3 Day 3	V 4 Day 7	V 5 Day 1 Mo 2	V 6 Day 2 Mo 2	V 7 Day 3 Mo 2	V 8 Day 7 Mo 2	V 9 Day 1 Mo 3	V10 Day 2 Mo 3	V 11 Day 3 Mo 3	V 12 Day 7 Mo 3	V 13-14 Mo 6 & 12
Physical Assessments	X				X				X				X	
Labs	X	X ^c		X		X ^c		X		X ^c		X		
24 hr urine gd	X	X ^a	X ^a			X ^a	X ^a			X ^a	X ^a			
Pain/QOL questionnaire	X				X ^e				X ^e				X ^e	X ^d
IV Ca-DTPA therapy		X				X				X				
IV Zn-DTPA therapy			X				X				X			

- a. Patients will begin 24hr urine collection immediately following therapy
- b. Assessments may be done by phone when patient lives greater than 3 hours away
- c. Urine pregnancy testing will be done on day one of therapy for WCBP

- d. Patients will be called to collect pain and QOL data at months 6 and 12
- e. Pain/QOL questionnaires will be filled out days 1-6 and returned day 7

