1.5 Dose Rationale and Risk/Benefits

The doses selected (1 gram each of Ca-DTPA and Zn-DTPA) are based on information in the package insert of these products for use as radionuclide decorporation agents.

It is worth emphasizing that DTPA (and other chelators in different GBCA products) represents the component that makes MRI contrast agents 'safe', and we will administer it in approximately 1/4 the standard dose of the MR contrast agents. As a side note, it should be observed that the total amount of DTPA ligand is approximately the same amount of free ligand that is delivered when a magnetic resonance angiogram is performed using Optimark as the contrast agent. Thus, the precedent exists for this in clinical practice, with the comparable intention of scavenging free Gd to minimize the potential for deposition.

2 Study Objectives

Primary Objective:

- To observe an increase in the elimination of Gd as measured by analysis of 24-hour urine collections.

Secondary Objective:

- To observe a measurable reduction or elimination of symptoms caused by administration of a GBCA.
- Evaluate chemokine mediators and function of the mononuclear phagocyte system prior to and after treatment with DTPA.

3 Study Design

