3.1 General Design

This is an open-label study. Patients will be evaluated at a baseline visit to determine eligibility and obtain informed consent before proceeding on to study-related procedures. Most patients coming for treatment will have had prior gadolinium testing greater than 30 days post MRI/contrast agent that shows an elevated result, thus eligibility for chelation therapy.

In addition to previous gadolinium testing, subjects will be instructed to perform a 24-hour urine collection (at visit 0) to determine a baseline for evaluating the elimination of gadolinium before initiating the first treatment.

At the first and subsequent chelation therapy visits, a baseline blood pressure will be obtained, an IV will be placed by Vascular Interventional Radiology (VIR) nursing staff, and 1L of normal saline will be connected. Initially, 2.5 mL of Ca-DTPA (1 g/5 mL) will be administered over a period of 1 minute. Five (5)

minutes post DTPA blood pressure will be collected again. The saline will then be administered at a rate of 300 mL/hr over 30 minutes with the patient seated and with hands lowered by their sides to allow the chelator to dwell slightly in the soft tissues of the hands and feet. The patient will then be positioned in a supine position on a hospital bed/gurney and the infusion rate will then be increased to 750 mL/hr over the next 60 minutes. With 10 minutes remaining (80 minutes after the start of infusion), the remaining 2.5 mL of Ca-DTPA will be administered I.V. over a period of 1 minute. The infusion of saline will continue another 9 minutes, and the I.V. line will then be removed. The patient will be instructed to drink plenty of fluids that evening. The following day, the treatment will be repeated using Zn-DTPA.

The patient will be instructed to collect 24-hour total urine samples beginning once chelation therapy starts, and bring back to the lab the following days.

The process will be repeated monthly, for a total of 3 chelation treatment time-points.

Patients will come to clinic for follow up to be assessed for adverse events one week following each treatment. Patients will be asked to fill out pain/QOL questionnaires and given a brief physical exam. Patients who live greater than 3 hours away will be assessed via phone call and instructed to get labs drawn locally. Patients may be advised to seek medical attention if the investigator feels any adverse reaction is not expected or is severe.

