5.5 Subject Compliance Monitoring

Subjects are treated and discharged from the clinic. They will be instructed to drink plenty of fluids, and collect urine for the following 24 hours to be returned the following day. Subjects will also have blood chemistries drawn the day following the second infusion for monitoring. Subject treatment will discontinue if they do not collect the 24 hour urine sample for testing following the infusion therapy, or refuse blood chemistry monitoring.

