5.9.4 Return or Destruction of Study Drug

At the completion of the study, there will be a final reconciliation of drug shipped, drug consumed, and drug remaining. This reconciliation will be logged on the drug reconciliation form, signed and dated. Any discrepancies noted will be investigated, resolved, and documented prior to return or destruction of unused study drug. Drug destroyed on site will be documented in the study files.

6 Study Procedures

6.1 **Visit 0-** The patient will be seen and evaluated by a UNC clinician regarding symptoms, assessments, a physical exam, a medication history and lab values up to one week prior to anticipated therapy start date. After agreeing to participate in the study, a coordinator will obtain informed consent signatures and the patient will be instructed to collect a 24-hour urine so that gadolinium can be measured for pre-treatment values.

6.2 **Visit 1-** The patient will come for infusion chelation therapy with Ca-DTPA to be done in the Clinical and Translational Research Center. Patient will void and have a baseline blood pressure taken before start of treatment. A urine pregnancy test will be performed if the subject is a woman of child-bearing potential. Blood samples will be collected by phlebotomy trained staff at the Clinical & Translational Research Center (CTRC) at UNC Memorial hospital. Patient blood samples will be obtained just prior to intravenous administration of Ca-DTPA or Zn-DTPA. The IV will be placed by nursing staff, and the infusion of normal saline will begin. The first injection of Ca-DTPA is performed by the investigator, or one of the co-investigators. Five (5) minutes post injection of Ca-DTPA another blood

pressure will be taken. Saline will continue for another 80 minutes, and the second injection of Ca-DTPA will be given by an investigator, followed by the last 10 minutes of saline infusion. IV will be discontinued, vitals checked, and patient will be discharged home. Patient will begin 24-hour urine collection once the infusion is started. They will be instructed to drink plenty of fluids. Analog pain scale sheets will be given to the subject to fill out starting with day 1 through day 6 post treatment, which will be returned on the day 7 visit. Urine is to be brought in on 2nd day of therapy.

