6.3 **Visit 2-** The patient subject will come for the second infusion therapy with Zn-DTPA. Patient will void and have a baseline blood pressure taken prior to initiation of therapy. Blood samples will be collected by phlebotomy trained staff at the Clinical & Translational Research Center (CTRC) at UNC Memorial hospital. Patient blood samples will be obtained just prior to intravenous administration of Ca-DTPA or Zn-DTPA. IV placement will be done by nursing staff, normal saline infusion started, and Zn-DTPA injections will be done by investigator or one of the co-investigators exactly as the day prior. Five (5) minutes post injection of Zn-DTPA another blood pressure will be taken. Another 24-hour urine sample will be collected beginning after chelation therapy is initiated, to be returned then next day.

6.4 **Visit 3-** The patient will return to the hospital to drop off 24 hour urine for gadolinium testing, as well as a creatinine clearance. Blood chemistries calcium, zinc, magnesium and manganese will be evaluated, along with BUN, creatinine, sodium, potassium, chloride, phosphorus and CO₂.

6.5 **Visit 4-** The patient subject will come for a follow up assessment by a clinician 1 week (+5 days) following IV therapy, where pain and overall health assessments will be performed. If the patient lives more than 3 hours away, a phone-call follow up will be done and questionnaires will be supplied to be filled out and emailed prior to leaving the infusion therapy. The second therapy session will be scheduled for the following month.

6.6. **Visit 5-** Patient will return for 2nd round of infusion therapy to be done exactly as first, with day one of Ca-DTPA including pregnancy testing on women of child-bearing potential and pain scale assessment sheets for the week. Blood samples will be collected by phlebotomy trained staff at the Clinical & Translational Research Center (CTRC) at UNC Memorial hospital. Patient blood samples will be obtained just prior to intravenous administration of Ca-DTPA or Zn-DTPA.

6.7 **Visit 6-** Patient returns for day two of infusion therapy with Zn-DTPA. Blood samples will be collected by phlebotomy trained staff at the Clinical & Translational Research Center (CTRC) at UNC Memorial hospital. Patient blood samples will be obtained just prior to intravenous administration of Ca-DTPA or Zn-DTPA

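### The events table and the visit text give different start times for all six post-infusion 24-hour urine collections

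*Combined protocol and SAP*

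**What the plan says.** Three places in the body start the post-infusion urine with treatment:

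- Section 3.1: patients are to "collect 24-hour total urine samples beginning once chelation therapy starts".
- Section 6.2 (Visit 1, Ca-DTPA): "Patient will begin 24-hour urine collection once the infusion is started".
- Section 6.3 (Visit 2, Zn-DTPA): "Another 24-hour urine sample will be collected beginning after chelation therapy is initiated".

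The bladder is emptied beforehand. Section 6.3 states "Patient will void and have a baseline blood pressure taken prior to initiation of therapy", and Section 6.2 has the same step. Sections 6.6 and 6.10 carry the round-1 procedure to rounds 2 and 3.

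Footnote a of the Time and Events Table (Section 15, Appendices) reads "Patients will begin 24hr urine collection immediately following therapy". It is attached to the urine cells for V1, V2, V5, V6, V9 and V10, which are all six post-infusion collections. The Visit 0 collection carries no footnote.

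Section 5.5 mentions treatment and discharge and then asks patients to "collect urine for the following 24 hours to be returned the following day". It gives no start time and can be read either way. For the day-1 sample, Section 6.2 adds "Urine is to be brought in on 2nd day of therapy".

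**The concern.** A session consists of two half-dose injections and a saline infusion, so the plain sense of the footnote is that collection starts when the session ends. The body text starts it at the beginning. The two rules disagree on whether urine passed during the session counts.

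These collections carry the primary objective in Section 2, "To observe an increase in the elimination of Gd as measured by analysis of 24-hour urine collections" (Section 3.3 lists the same measure as a secondary endpoint). Section 7.2 makes the main aim estimating the size and spread of the effect for a future trial, through paired changes from baseline. Leaving out session urine tends to understate elimination against a full 24-hour Visit 0 baseline. If some patients or rounds follow the text and others the footnote, the paired differences also gain noise that has nothing to do with the drug. The two-fold rise in Section 3.3 is an expectation and not a decision rule, so what is at stake is a distorted estimate and not a failed test.

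**Working it through.** The documents give no figure of their own to reproduce here. The check sets the passages side by side and then sizes the gap.

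**1. Number of collections affected.** Footnote a is on V1, V2, V5, V6, V9 and V10: 6 per subject, or 6 × 20 = 120 in the planned study.

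**2. Distance between the two start times (one session).**

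| Source | Sum | Minutes | Share of 1440 min |
|---|---|---|---|
| Section 3.1 | 80 + 1 + 9 | 90 | 90/1440 = 6.25% |
| Section 5.2 | 90 + 1 + 9 | 100 | 100/1440 = 6.94% |

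Sections 3.1 and 5.2 disagree on session length; both are used as a range, without choosing. Section 6.2, read as 5 + 80 + 10 = 95 minutes, falls inside it. By Section 3.1 the session includes both injections and 300 mL/h × 0.5 h + 750 mL/h × 1 h = 900 mL of saline.

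**3. Day-1 collections (V1, V5, V9).** The container is due on day 2 and no day-2 clock time is fixed. If day 2 starts at the same clock time as day 1, a collection begun at session end has 24 − 1.5 = 22.5 h or 24 − 1.67 = 22.33 h left. Otherwise a full 24 h runs 90 to 100 minutes into the Zn-DTPA session. It reaches 24 h without overlap only if day 2 starts at least 1.5 to 1.67 h later in the day. On the same schedule, the body text gives 24 h with no overlap.

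**4. Day-2 collections (V2, V6, V10).** No infusion follows, so nothing cuts them short. If session urine is discarded, the 24-hour window is only shifted: the loss is nil if excretion is even and arises only if it is front-loaded.

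**5. Effect on the fold-change.** The documents do not say how Gd excretion is spread over the day, so everything below is an assumption.

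*Even excretion, truncated day-1 collection, all session urine discarded.* Reading = R × (1 − share lost):

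- 90 min: 2.0 × (1 − 0.0625) = 1.875
- 100 min: 2.0 × (1 − 0.0694) = 1.861

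*Assumed net loss L of 24-hour Gd.* Reading = R × (1 − L):

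| L | True 2.0-fold | True 2.5-fold |
|---|---|---|
| 5% | 1.90 | 2.38 |
| 10% | 1.80 | 2.25 |
| 20% | 1.60 | 2.00 |
| 30% | 1.40 | 1.75 |

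*Front-loaded sketch.* Suppose the excess Gd leaves by first-order excretion, half from time 0 and half from the second injection at 80 minutes (Section 3.1), and all session urine is lost. With k = ln 2 / half-life, the excess excreted by time t is E(t) = 0.5(1 − e^(−kt)) + 0.5(1 − e^(−k·max(0, t − 80))). The fraction kept is g = [E(1530) − E(90)] / E(1440), and a true 2.0-fold rise reads 1 + g. The half-life is not in the documents.

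| Assumed half-life (h) | Excess lost | True 2.0-fold reads |
|---|---|---|
| 0.5 | 54% | 1.46 |
| 1 | 38% | 1.62 |
| 2 | 23% | 1.77 |
| 4 | 13% | 1.87 |
| 8 | 6% | 1.94 |

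Because the sketch treats all session urine as lost, each row is an upper bound on the loss for its half-life.

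**The case against.** The best reply is that the practical risk is small. Three body passages agree, the pre-infusion void fits them, and Section 6 is the working instruction at a single centre; the outlier is one line under a table. That makes the intended start fairly clear, but no passage says which text governs, and a stated rule covering all six collections can be followed as written. Mixed practice is a possibility, not something the documents show. No listed procedure asks for start and stop times, so it could not be detected afterwards.

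The second reply is that the loss is assumed. This stands. Urine still in the bladder at session end is caught, and the documents describe no void during the session. If nobody voids, session urine enters the collection under either rule. A footnote collection run for a full 24 h after the session then covers 24 + 1.5 = 25.5 h to 24 + 1.67 = 25.67 h of urine production. With even excretion, a true 2.0-fold rise would read 2.0 × 25.5/24 = 2.125 to 2.0 × 1540/1440 = 2.139. The direction of error therefore depends on each patient's voiding, which is itself a reason to fix the window.

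Third, truncation or overlap can arise under the body text too, if day 2 starts earlier in the day than day 1. That is true; it is why the fix also sets an end point. Ending at the day-2 void can leave some collections short, and with 20 subjects exclusions could leave few pairs. Flagged collections should therefore stay in the main analysis and be dropped only in the sensitivity analysis.

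**Conclusion.** The contradiction is real and the footnote is wrong as written. It changes what the primary-objective measurement contains in every post-infusion collection, and for V1, V5 and V9 it does not fit the day-2 return when day 2 starts at the same clock time.

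Confidence is high for the conflict and for the size of the gap (90 to 100 minutes). It is low for the resulting bias, which rests on three things the documents do not give: the time course of Gd excretion, voiding during the session, and day-2 start times. The readings of a true 2.0-fold rise in the working show plausible scale and are not estimates. The correction should be made before enrolment or, failing that, before the urine data are analysed.

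**What to change.** - **Footnote a:** reword it to match Sections 3.1, 6.2 and 6.3. Collection begins at the start of infusion, after the pre-infusion void already in Sections 6.2 and 6.3, and includes all urine passed during the session.
- **Section 5.5:** state the same start time.
- **Day-1 samples (V1, V5, V9):** state that they end no later than the void before the day-2 infusion.
- **CRF:** record start and stop times for each collection.
- **Section 7.2:** flag collections that are short or overlap the next session, and repeat the paired Gd comparison without them as a sensitivity analysis.

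The cost is a wording change in two places plus the day-1 end point, two recorded times per collection and one extra analysis. No visits, samples or assays are added.
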